7.2 Methods and Timing for Assessing, Recording, and Analyzing Safety Parameters

Timing of assessment and reporting of adverse events are detailed in items 7.3 and 7.4 below. We will utilize a Data Safety and Monitoring Committee and will immediately report any unanticipated or adverse events affecting subjects or others to the Institutional Review Board (IRB) of the University of California, San Diego to determine whether further information or protocol changes are needed. Any study modifications required by the IRB would be reported to the NCCAM/NIH program officer immediately.

7.3 Adverse Events and Serious Adverse Events

An adverse event (AE) is any untoward medical occurrence in a subject during participation in the clinical study or with use of the experimental agent being studied. An adverse finding can include a sign, symptom, abnormal assessment (laboratory test value, vital signs, electrocardiogram finding, etc.), or any combination of these.

A serious adverse event (SAE) is any adverse event that results in one or more of the following outcomes:

- Death

- A life-threatening event
- Inpatient hospitalization or prolongation of existing hospitalization
- A persistent or significant disability/incapacity
- A congenital anomaly or birth defect
- An important medical event based upon appropriate medical judgment

AEs will be categorized according to the likelihood that they are related to the study intervention as follows:

0 – Definitely unrelated:	AE is clearly not related to the investigational agent(s)
1 – Unlikely:	AE is doubtfully related to the investigational agent(s)
2 – Possibly related:	AE may be related to the investigational agent(s)
3 – Probably related:	AE is likely related to the investigational agent(s)
4 – Definitely related:	AE is clearly related to the investigational agent(s)

All AEs (and SAEs) will be recorded by the study coordinator, research associate or other staff member as they occur. Reports that include onset time, duration, severity, etc., will be sent to PI for review to determine actions to be taken, relatedness to study and monitoring of outcomes.

Mood ratings and side effects checklists will be utilized to assess treatment safety.

7.4 Reporting Procedures

As detailed in the Data and Safety Monitoring Plan (DSMP) for an Independent Monitoring Committee, AEs (and SAEs) will be labeled by level of severity in accordance with the grading system stipulated in the U.S. Department of Health and Human Services' Common Terminology Criteria for Adverse Events (CTCAE) – Version 4.0 (v4.03: June 14, 2010).¹ Grades range from 1 to 5 and are based on the AE's impact on the patient as 1) Mild, 2) Moderate, 3) Severe, 4) Life-threatening, and 5) Death. Attribution of each AE will be determined by PI according to the above criteria.

AEs will be followed up weekly for 3 months, once every 2 weeks for 2 months, and once per month for 1 month (total of 6 months).

The Independent Monitoring Committee (IMC), composed of a clinician with expertise in women's mental health and the reproductive cycle, a physician with expertise in clinical trials and a biostatistician will review adverse event rates yearly. A yearly Study Safety Report listing individual AEs, frequency/severity of treatment-related side effects and out-of-range scores will be provided to the IMC, the UCSD IRB and NIH/NCCAM.

¹ U.S. Department of Health and Human Services, National Institutes of Health, National Cancer Center. Common Terminology Criteria for Adverse Events (CTCAE) Version 4.0 – Published: May 28, 2009 (v4.03: June 14,2010) http://evs.nci.nih.gov/ftp1/CTCAE/CTCAE_4.03_2010-06-14_QuickReference_8.5x11.pdf

SAEs that are unanticipated, serious, and possibly related to the study intervention will be reported to the IMC, IRB and NCCAM in accordance with requirements.

- Unexpected fatal or life-threatening AEs related to the intervention will be reported to the NCCAM Program Officer within 7 days. Other serious and unexpected AEs related to the intervention will be reported to the NCCAM Program Official within 15 days.
- Anticipated or unrelated SAEs will be handled in a less urgent manner but will be reported to the IMC, IRB, NCCAM, and other oversight organizations in accordance with their requirements. In the annual AE summary, the Independent Monitor Report will state that they have reviewed all AE reports.

7.5 Followup for Adverse Events

AEs will be followed weekly for 3 months, once every 2 weeks for 2 months, and once per month for 1 month (total of 6 months).

8. INTERVENTION DISCONTINUATION

If complications develop from the urine collection, sleep, activity or light studies, the procedure would be discontinued and all appropriate measures taken to provide the necessary care and follow up (unless otherwise requested by patient).

Participation in research is entirely voluntary. Patients may refuse to participate or withdraw at any time without jeopardy to the medical care they will receive at this institution or loss of benefits to which they are entitled. The investigator also may withdraw patients from participation if they become pregnant or otherwise lose qualification for participation (see sections 4.1 and 4.2 for inclusion and exclusion criteria, respectively). The PI can

withdraw patients from the study without their consent if they fail to comply with important study requirements, such as keeping appointments or if they become so ill that they need to be referred for outside treatment.

9. STATISTICAL CONSIDERATIONS

9.1 General Design Issues

The design is a randomized cross-over contrasting LWT+AM bright light vs. EWT+PM bright light administered in the luteal phase of two separate menstrual cycles, and preceded by 2 evaluation months. To lessen the patient's burden, the 1-night EWT or LWT and the following 7-day BWL interventions will be conducted at home, given at a fixed point in each menstrual cycle, from day 1 to 7 after the mid-cycle LH surge. We anticipate that LWT+7 days of AM BWL (vs. EWT+PM BWL) will produce much greater mood benefits and larger physiological responses, than the one-time light pulses used in our earlier phase-shift studies.

The wake therapy and light interventions proposed in this application are based on our previous studies in PMDD and key published experiments by other investigators that indicate that the combined interventions are efficacious in other mood disorders after one week of treatment and maintained at 9-months follow-up. To provide optimal timing of interventions, we will administer wake therapy in the early-night vs. late-night and light pulses in the AM vs. PM at selected times in relation to sleep (within 30 min of waking and 90 min before sleep onset, respectively).

A crossover treatment design is employed to compare LWT+AM BWL vs. EWT+PM BWL responses within the same individual. As wake interventions lose effectiveness after 1 day, and light treatment effects after 3-4 days, we anticipate minimal carry-over effects of the wake plus light interventions administered a month apart. To further ensure no carry-over effects, there will be a month of no-intervention between the 1st and 2nd treatments. Because our previous studies clearly indicated differences between PMDD and NC subjects occurred primarily in the luteal menstrual cycle phase, we will treat during this menstrual cycle phase rather than in the follicular phase.

Hypothesis (H) 1: For PMDD patients in the luteal phase, LWT+AM BWL, compared with EWT+PM BWL, will A) Decrease scores on SIGH-SAD, BDI, BAI, and DMR, and increase global assessment of treatment effectiveness from baseline to post-intervention; B) Phase-advance urinary melatonin timing measures (acrophase, onset and offset time) in relation to clock time and to sleep measures (onset, end time and mid-sleep times); C) The magnitude of the phase-advance (B, above) will correlate with the magnitude of the symptom changes (A, above) by linear regression.

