9.2 Sample Size and Randomization

For our primary outcome measures of mood, based on our earlier data reflecting

seven days of light exposure alone² (i.e., without the ‘priming’ effect of wake therapy), we predict the following changes in mood in PMDD subjects (N = 40) after Late Wake Therapy plus AM Light vs. Early Wake Therapy plus PM Light: A significantly greater improvement (decrease in raw score) will be detected at the p = .05 level with (a) 71% power in Hamilton Rating Scale for Depression (HRSD) Score (Mean difference 3.15±9; effect size = .324); (b) > 99% power in atypical score (Mean difference 4.45±5; effect size = .78); (c) > 99 % power in Structured Interview Guide for the Hamilton Depression Rating Scale, Seasonal Affective Disorders (SIGH-SAD) Items (Mean difference 7.0±11; effect size = .627); (d) 86% power in Beck Depression Inventory (BDI) score (Mean difference 6.30±15; effect size = .378).

For the recovery criterion of $\geq 50\%$ decrease from baseline (Chi Square analyses): (a) 97% power for HRSD score (difference in proportions: .44); (b) 70% power for atypical score (difference in proportions: .30); (c) 86% for SIGH-SAD score (difference in proportions: .325); and (d) 93% power for BDI score (difference in proportions: .40). For the remission criterion of reduction to a score of ≤ 8 (Chi Square analyses): (a) 89% power for the SIGH-SAD score; (b) 44% power for the BDI score. All tests are two-tailed.

We also performed power analyses for the primary hypotheses, incorporating the longitudinal nature of the design for the proposed Random Regression model (also known as Multilevel Models, or Growth Curve Models). Procedures describes by Hedeker et al.⁶⁹ for Random Regression Models, with the above data, was used for the proposed study to estimated needed sample size. We assume a Type-I error level (alpha-level) of 0.05, drop-out rate of 10% to 15% and an autoregressive covariance structure, with correlation between sequential assessments set at 0.45 (based on our previous data). We are confident based on our results from these two separate approaches that the proposed study will have minimum power of 80% to yield a statistically significant result for a medium effect size. Here, medium effect size is defined as a treatment difference increasing linearly from 0 at baseline to .5 SD units at the last time point. Type 1 error will be controlled by correcting the p-value per domain.

Treatment Assignment Procedures

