9.5 Outcomes

9.5.1 Primary Outcome

- Treatment-Related Mood Rating Changes from Baseline (month 2) to post intervention (months 3,5) :
Mood ratings include Hamilton Rating Scale for Depression (HRSD), Beck Depression Inventory (BDI), atypical depression symptoms as part of the Structured Interview Guide for the Hamilton Depression Rating Scale, Seasonal Affective Disorders version (SIGH-SAD), Beck Anxiety Inventory (BAI), mania ratings, the Psychological General Well-Being Index (PGWI) and daily mood self-ratings (DMR) that include core PMDD symptoms of anxiety and irritability as required during diagnostic evaluation, before, during and after each wake and light intervention at the same time of day (between 15:00-17:00 h). To assess more acute effects on mood that may occur more rapidly during the wake interventions, subjects will complete DMRs twice daily beginning the evening before the wake therapy intervention and continuing until the morning after the recovery night of sleep.
- Treatment-Related Urinary 6-sulfatoxymelatonin (6-SMT) Changes from Baseline (month 2) to post intervention (months 3,5) :
6-SMT is a principal melatonin metabolite that is abundant in urine, well correlated with plasma melatonin, and serves as an excellent marker for circadian phase response.
- Treatment-related changes in objective and subjective sleep measures:
Using actigraphy, we will obtain objective measures of the sleep/wake cycle to ensure appropriate sleep/wake times during wake therapy, and during the light interventions as it is an important biological rhythm with which to compare the intervention-induced melatonin rhythm changes. To assess subjective sleep quality, we will use the Pittsburgh Sleep Quality Index (PSQI) and a visual analogue scale.

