Specifically, data for hypothesis 1.A. will be analyzed using a Random Regression Model (RRM), a generalized linear model described by Gibbons et al.,⁷⁴ Hedeker et al.⁶⁹ and Laird.⁷⁵ The random effects method has several advantages over more traditional analytic approaches such as a change score, end-point or repeated measures analysis of variance. This method allows the inclusion of subjects with missing data or those who were terminated early in the study, without relying on data imputation procedures. This method provides an estimate of the individual variability around the population trend, the variability of the individual intercepts (baseline values) and slopes (changes across time), and the correlation between them. A fully saturated treatment by time model will be utilized for inference. Co-variance structure will be chosen based on Akaike's Information Criterion (AIC). Random treatment effects also will be evaluated for importance based on the model AIC. This plan allows for any group level effects to be incorporated into the model. Denominator degrees of freedom will be calculated using the Kenward-Roger small sample correction. All subjects will be included in the analyses, and we will not focus only on subjects who complete the study. Our methods for data analyses include all subjects with any valid data points in the analyses. Secondary analyses will be performed on data from completers. Type 1 error will be controlled by correcting the p-value per domain. For hypothesis 1.B, an individual's slope for each of the dependent variables listed above will be calculated and will be used for correlational analysis using the Pearson method. In addition, we will examine the number of responders. The operational definition of the criteria for

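### The primary mood scales differ between Hypothesis 1.A, Section 9.5.1 and the power section, so the promised per-domain correction has no fixed mood family and no named method

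*Combined protocol and SAP*

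**What the plan says.** Three current sections each describe the primary mood outcome.

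- **Section 9.1, Hypothesis 1.A:** "Decrease scores on SIGH-SAD, BDI, BAI, and DMR", plus an increase in the global assessment of treatment effectiveness. Five measures.
- **Section 9.5.1, Primary Outcome:** "Mood ratings include Hamilton Rating Scale for Depression (HRSD), Beck Depression Inventory (BDI), atypical depression symptoms" (described there as part of the SIGH-SAD), then BAI, mania ratings, PGWI and DMR. Seven measures.
- **Section 9.2:** under a lead-in that calls them the primary mood measures, power is given for HRSD, atypical score, SIGH-SAD and BDI. Four measures, the first with "71% power in Hamilton Rating Scale for Depression (HRSD) Score".

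Section 9.5.2 classes the global assessment as secondary. The responder analysis in Section 9.6 uses HRSD, SIGH-SAD and BDI.

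On multiplicity, Section 9.6 says: "Type 1 error will be controlled by correcting the p-value per domain". Section 9.2 makes the same promise. Neither defines a domain, lists its members or names the procedure. The power figures are set at the unadjusted level: "We assume a Type-I error level (alpha-level) of 0.05" for the mixed-model calculation, p = .05 for the scale-by-scale figures, and "All tests are two-tailed".

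**The concern.** A per-domain correction needs two things fixed in advance: which scales belong to the domain, and how the p-values are adjusted. The plan fixes neither for mood.

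Membership matters more than the divisor. HRSD is primary in Sections 9.5.1 and 9.2 but is not a separate endpoint in Hypothesis 1.A. The SIGH-SAD total is in Hypothesis 1.A and Section 9.2, while Section 9.5.1 names only its atypical symptoms. PGWI and mania ratings are primary only in Section 9.5.1, and the global assessment only in Hypothesis 1.A. A positive result on any of these could be reported as primary or secondary by citing a different section, and that choice could be made after the results are known. For the scales that the lists share, the size of the family sets the threshold, so a borderline p-value can pass under one list and fail under another.

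**Working it through.** **1. The lists side by side**

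| Measure | Hyp. 1.A (9.1) | 9.5.1 | 9.2 power |
|---|---|---|---|
| BDI | yes | yes | yes |
| SIGH-SAD total | yes | not as a total | yes |
| HRSD | no | yes | yes |
| Atypical score | no | yes | yes |
| BAI | yes | yes | no |
| DMR | yes | yes | no |
| PGWI | no | yes | no |
| Mania ratings | no | yes | no |
| Global assessment | yes | no (secondary, 9.5.2) | no |
| Count | 5 | 7 | 4 |

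Only BDI is named on all three. HRSD and atypical score stand beside the SIGH-SAD total, which contains them, only in the Section 9.2 list. Hypothesis 1.A has the total without its parts, and Section 9.5.1 has the parts without the total.

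**2. Threshold by list**

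Assumptions, because the plan is silent: Bonferroni, and all mood scales in one domain. Threshold = .05/k.

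- k = 4 (Section 9.2): .05/4 = .0125
- k = 5 (Hypothesis 1.A): .05/5 = .0100
- k = 7 (Section 9.5.1): .05/7 = .0071

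A BDI result of p = .009 is significant under Section 9.2 and Hypothesis 1.A and not under Section 9.5.1. Outside the band .0071 to .0125, the divisor does not change the verdict for a scale on all three lists.

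**3. The plan's own power figures**

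Inputs from Section 9.2: N = 40, two-tailed .05, effect sizes .378 (BDI) and .627 (SIGH-SAD). In a paired t-test with 39 df, the noncentrality is effect size × √40:

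- BDI: .378 × 6.325 = 2.391. Critical t is 2.023 and power is 64.5%, against 86% stated.
- SIGH-SAD: .627 × 6.325 = 3.965. Power is 97.2%, against more than 99% stated.

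The stated figures do not reproduce on this basis. That is a separate matter, and the present point does not rest on it. The uncorrected 64.5% is shown so that the gap from 86% is not attributed to multiplicity.

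**4. Power at each threshold, same test**

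| k | alpha | critical t | BDI | SIGH-SAD |
|---|---|---|---|---|
| 1 | .05 | 2.023 | 64.5% | 97.2% |
| 4 | .0125 | 2.619 | 42.0% | 90.4% |
| 5 | .0100 | 2.708 | 38.7% | 88.9% |
| 7 | .0071 | 2.839 | 34.1% | 86.2% |

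Going from 4 to 7 scales costs 42.0 − 34.1 = 7.9 points for BDI and 90.4 − 86.2 = 4.2 for SIGH-SAD.

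**5. Accepting the stated 86% for BDI**

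Normal approximation: the implied noncentrality is 1.960 + 1.080 = 3.040. Power is Φ(3.040 − z), with z = 2.498, 2.576 and 2.690 for k = 4, 5 and 7. This gives 70.6%, 67.9% and 63.7%, a spread of about 7 points.

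**The case against.** Several objections have force.

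**The Section 9.2 list may not be a definition.** It is introduced as resting on earlier data and may show only the scales for which such data existed. This stands in part: the text does call them primary, but the firmest conflict is Hypothesis 1.A against Section 9.5.1, and that conflict remains if Section 9.2 is set aside.

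**The domains can be inferred.** The three bullets of Section 9.5.1 (mood, melatonin, sleep) are a natural reading. That would settle the number of domains, but not which scales make up the mood domain or how they are corrected. A finer split, say into depression, anxiety and well-being, would change every threshold above.

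**The calculation is not the planned analysis.** The plan uses a random regression model with Kenward-Roger degrees of freedom and names no correction. This stands: the paired t-test and Bonferroni show scale only.

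**Stronger readings are tempting, and the documents do not support them.**

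- A reader might infer that significance generally turns on the list. For a scale on all three lists, the divisor matters only for p between .0071 and .0125.
- A reader might infer that multiplicity takes BDI power from 86% to 42%. In the same test, the step from 86% to 64.5% has nothing to do with the correction.
- A reader might infer that the lists in general count the same items twice. Only the Section 9.2 list does.
- A reader might infer that the documents single out SIGH-SAD and BDI as the rightful primary pair. Only BDI is named on all three lists, and BAI and DMR are in both Hypothesis 1.A and Section 9.5.1.

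**Conclusion.** The inconsistency is real and should be corrected. Hypothesis 1.A and Section 9.5.1 give different primary mood measures, Section 9.2 gives a third set, and the global assessment is inside the primary hypothesis yet secondary in Section 9.5.2. The promised Type I error control cannot be carried out as written, because its mood family and its method are both open.

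The main consequence is that whether HRSD, the SIGH-SAD total, PGWI or the global assessment can carry a primary claim depends on the section followed. The numerical effect of list length alone is modest: about 8 points of power for BDI and 4 for SIGH-SAD, and a change of verdict only in a narrow band of p-values. These figures assume Bonferroni, a single mood domain, a paired t-test at N = 40 and the effect sizes in Section 9.2. The membership problem needs none of those assumptions.

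**What to change.** Before unblinding:

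1. Adopt one closed list of primary mood measures and use it identically in Sections 9.1, 9.2, 9.5.1 and 9.6. Do not place a total beside its own components. Report mania ratings as safety, since Sections 6.2.2 and 6.2.4 collect them to detect manic symptoms brought on by treatment.
2. Give the global assessment one status throughout.
3. State the domains, for example the three bullets of Section 9.5.1, and the members of each, including melatonin and sleep.
4. Name the correction, for example Holm.
5. Restate power at the corrected alpha.

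One workable example is SIGH-SAD total and BDI with Holm over two, the other scales being secondary. At the stricter Holm step (.05/2 = .025), the paired calculation gives 52.9% for BDI and 94.5% for SIGH-SAD. The sponsor may prefer another closed list, for instance one that keeps DMR because it carries the core PMDD symptoms; if so, the DMR score to be tested should be specified.

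The cost is wording only, with no added visits or data. The downside is that scales left off the list can support only secondary claims, and the stated powers will look less favourable.

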9.2 Sample Size and Randomization

For our primary outcome measures of mood, based on our earlier data reflecting

seven days of light exposure alone² (i.e., without the ‘priming’ effect of wake therapy), we predict the following changes in mood in PMDD subjects (N = 40) after Late Wake Therapy plus AM Light vs. Early Wake Therapy plus PM Light: A significantly greater improvement (decrease in raw score) will be detected at the p = .05 level with (a) 71% power in Hamilton Rating Scale for Depression (HRSD) Score (Mean difference 3.15±9; effect size = .324); (b) > 99% power in atypical score (Mean difference 4.45±5; effect size = .78); (c) > 99 % power in Structured Interview Guide for the Hamilton Depression Rating Scale, Seasonal Affective Disorders (SIGH-SAD) Items (Mean difference 7.0±11; effect size = .627); (d) 86% power in Beck Depression Inventory (BDI) score (Mean difference 6.30±15; effect size = .378).

For the recovery criterion of $\geq 50\%$ decrease from baseline (Chi Square analyses): (a) 97% power for HRSD score (difference in proportions: .44); (b) 70% power for atypical score (difference in proportions: .30); (c) 86% for SIGH-SAD score (difference in proportions: .325); and (d) 93% power for BDI score (difference in proportions: .40). For the remission criterion of reduction to a score of ≤ 8 (Chi Square analyses): (a) 89% power for the SIGH-SAD score; (b) 44% power for the BDI score. All tests are two-tailed.

We also performed power analyses for the primary hypotheses, incorporating the longitudinal nature of the design for the proposed Random Regression model (also known as Multilevel Models, or Growth Curve Models). Procedures describes by Hedeker et al.⁶⁹ for Random Regression Models, with the above data, was used for the proposed study to estimated needed sample size. We assume a Type-I error level (alpha-level) of 0.05, drop-out rate of 10% to 15% and an autoregressive covariance structure, with correlation between sequential assessments set at 0.45 (based on our previous data). We are confident based on our results from these two separate approaches that the proposed study will have minimum power of 80% to yield a statistically significant result for a medium effect size. Here, medium effect size is defined as a treatment difference increasing linearly from 0 at baseline to .5 SD units at the last time point. Type 1 error will be controlled by correcting the p-value per domain.

Treatment Assignment Procedures

We will study subjects pre- and post-intervention to determine the optimal phase-relationship between melatonin and sleep. Using a randomized cross-over design, PMDD and NC in the luteal phase will receive either 1) one night of LWT (sleep 21:00-01:00 h, followed by wakefulness) plus 7 days of AM BWL (light-emitting diode-LED administered for 60 minutes, starting within 30 minutes of habitual wake time) or 2) EWT (wakefulness until 03:00 h, then sleep 03:00-07:00 h) plus 7 nights of PM BWL (administered 90 minutes before habitual sleep onset, for 60 minutes). Subjects will be cross-over to the other treatment in the luteal phase of their next menstrual cycles after one month of washout period.

Study statistician, [name], will prepare randomization table prior to startup of

² Parry BL, Berga SL, Mostofi N, Klauber MR, Resnick A. Plasma melatonin circadian rhythms during the menstrual cycle and after light therapy in premenstrual dysphoric disorder and normal control subjects. *J Biol Rhythms*. 1997;12(1):47-64.

the study.

For blinding, see section 6.2.3 above.

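### Section 9.2: the stated HRSD (71%) and BDI (86%) powers do not follow from the printed two-tailed inputs, three effect sizes do not match mean/SD, and 48 recruits at 20% drop-out give about 38 completers, not 40

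*Combined protocol and SAP*

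**What the plan says.** Section 9.2 bases its first set of power figures on earlier data from seven days of light alone, with N = 40 and the .05 level. The four continuous-score statements are:

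- HRSD: "a) 71% power in Hamilton Rating Scale for Depression (HRSD) Score (Mean difference 3.15±9; effect size = .324"
- Atypical score, stated power above 99%: "power in atypical score (Mean difference 4.45±5; effect size = .78"
- SIGH-SAD, stated power above 99%: "Items (Mean difference 7.0±11; effect size = .627"
- BDI: "86% power in Beck Depression Inventory (BDI) score (Mean difference 6.30±15; effect size = .378"

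The next paragraph, on response and remission proportions, closes with "All tests are two-tailed". Section 9.1 fixes the comparison as within-woman: "A crossover treatment design is employed to compare LWT+AM BWL vs. EWT+PM BWL responses within the same individual". Section 9.2 later says "Type 1 error will be controlled by correcting the p-value per domain".

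A second, separate calculation in 9.2 uses a random regression model. It assumes a correlation of .45 between sequential assessments and a "drop-out rate of 10% to 15" per cent. From the two approaches together, 9.2 concludes that power is at least 80% for a difference growing to .5 SD.

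The Précis (Sample Size and Population) plans 48 recruits to reach 40 completers, allowing for 20% drop-out. The Précis (Design and Outcomes) has 40 women randomized, and section 3 has forty recruited.

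**The concern.** Section 9.2 prints the sample size, alpha, sidedness, mean difference, a ± figure and an effect size. A reader should be able to turn these into the stated powers, and for HRSD and BDI cannot. Section 9.5.1 lists both among the primary mood ratings. If their true power is nearer 55% and 70% than 71% and 86%, a null result on either would be read as stronger evidence of no difference than it is.

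The effect sizes raise a related doubt. Three of the four disagree with the mean and SD printed beside them, so it is unclear which numbers entered the calculation. The recruitment figure is a smaller matter of the same kind: the completer target does not follow from the drop-out rate attached to it.

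**Working it through.** **Inputs.** n = 40, alpha = .05, two-sided (9.2); within-woman comparison (9.1); means, ± values and effect sizes as printed in 9.2. First reading: ± is the SD of the within-woman difference.

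**Formula.** Power of a two-sided paired t-test from the noncentral t distribution, df = 39, noncentrality d × √40, critical value 2.023. I ran it with d = mean/SD and with d = the printed effect size.

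| Score | mean/SD | Printed effect size | Power from mean/SD | Power from effect size | Stated |
|---|---|---|---|---|---|
| HRSD | 3.15/9 = .350 | .324 | 57.9% | 51.5% | 71% |
| Atypical | 4.45/5 = .890 | .78 | >99.9% | 99.8% | >99% |
| SIGH-SAD | 7.0/11 = .636 | .627 | 97.5% | 97.2% | >99% |
| BDI | 6.30/15 = .420 | .378 | 73.6% | 64.5% | 86% |

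Only the atypical score reproduces. The gaps are 71 − 57.9 = 13.1 to 71 − 51.5 = 19.5 points for HRSD, and 86 − 73.6 = 12.4 to 86 − 64.5 = 21.5 points for BDI. On this reading the stated powers need d = .4075 and .4930. That means difference SDs of 3.15/.4075 = 7.7 (printed 9) and 6.30/.4930 = 12.8 (printed 15).

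**Attempts to recover 71% and 86%.**

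- *All 48 recruits analysed, two-sided:* HRSD 59–66%, BDI 73–81%. Does not recover them.
- *± as a per-treatment SD, with the only printed correlation.* The paired effect is d/√(2(1 − r)). With r = .45, HRSD is 48–54% and BDI 60–70%. Further away.
- *± as a per-treatment SD, with r chosen to fit.* From mean/SD, HRSD needs r = .631 and BDI .637. At r = .634 the powers are HRSD 71.3%, BDI 85.7%, SIGH-SAD 99.6%, atypical >99.9%. From the effect sizes, r = .684 and .706 are needed; at r = .695, HRSD is 72.5% and BDI 84.7%. Close, but no such correlation is printed.
- *One-sided .05, normal approximation, on mean/SD.* HRSD 71.5%, BDI 84.4%, SIGH-SAD 99.1%. Close, but contrary to the two-tailed statement. On the printed effect sizes it gives only 65.7% and 77.2% for HRSD and BDI.
- *Two-sided paired t with 54 women on mean/SD.* HRSD 71.4%, BDI 85.8%, SIGH-SAD 99.6%. Close, but contrary to N = 40.

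**Effect sizes.** The SD implied by mean divided by effect size is 9.72 for HRSD (printed 9), 5.71 for atypical (5), 11.16 for SIGH-SAD (11) and 16.67 for BDI (15). Ordinary rounding explains SIGH-SAD only. If SDs were truncated to whole numbers, the possible effect sizes are:

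- HRSD: 3.15/10 to 3.15/9 = .315–.350, which contains .324
- Atypical: 4.45/6 to 4.45/5 = .742–.890, which contains .78
- BDI: 6.30/16 to 6.30/15 = .394–.420, which excludes .378

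So BDI cannot be reconciled by rounding or truncation.

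**Recruitment.** 48 × .80 = 38.4 completers; 40/.80 = 50 recruits. The figure 48 equals 40 × 1.2 and covers 1 − 40/48 = 16.7% drop-out. At the rates in 9.2, 48 × .90 = 43.2 (10%) and 48 × .85 = 40.8 (15%).

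**The case against.** The strongest reply is that 9.2 never says what ± means and names no test for the mean comparisons. If ± is a per-treatment SD, a single correlation near .63 recovers all four powers two-sided, and HRSD and BDI separately need almost the same value (.631 and .637). That looks as much like an unprinted input as a miscalculation, and the earlier study that would settle it is not in the documents. This stands, and it limits the finding to non-reproducibility: the lower powers are conditional on the difference-SD reading. Nor should any one explanation be favoured, since three different routes come close and each needs something that 9.2 contradicts or omits.

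Second, these simple powers are only one of two approaches. The random regression calculation, which matches the planned model in 9.6, supports at least 80% for a .5 SD effect. That claim is untouched here. But 9.2 rests its confidence on both approaches, and one of them cannot be checked.

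Third, the recruitment gap is two women, 48 is enough at 15% drop-out, and a recruitment allowance need not equal a modelling assumption. Sections 6.2.6, 9.3 and 9.6 also keep women with partial data in the analysis. All fair: the slip affects the stated completer target rather than the analysed N. Still, 48 does not deliver 40 completers at the 20% printed beside it.

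**Conclusion.** The concern holds. No two-tailed calculation using the printed N, the printed SDs or effect sizes, and the one printed correlation yields 71% for HRSD or 86% for BDI.

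- If ± is the SD of the within-woman difference, power is 52–58% for HRSD, 64–74% for BDI and about 97% for SIGH-SAD. All are before the per-domain p-value correction, which would lower them further.
- If ± is a per-treatment SD, the stated powers may be right, but the correlation they depend on (about .63 from mean/SD, about .70 from the effect sizes) is missing.

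The documents do not show which reading applies. The BDI effect size is inconsistent with its own mean and SD on any rounding convention; those for HRSD and atypical score fit only if the SDs were truncated. The completer shortfall is one or two women and is the minor part.

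**What to change.** Keep N = 40. In section 9.2:

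1. State whether ± is the SD of the within-woman difference or a per-treatment SD, and name the test.
2. Print one consistent mean difference, SD and effect size for each score.
3. If ± is the difference SD, replace 71% and 86% with about 58% and 74% (or 52% and 64% if the printed effect sizes are the correct inputs), and give SIGH-SAD as about 97%.
4. Keep 71% and 86% only if the earlier data supply the supporting correlation. Print it with matching effect sizes; do not choose it to fit the stated powers.
5. If the figures came from a one-sided calculation, recompute them two-tailed.
6. Note that these powers precede the per-domain correction.

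In the Précis, say that 48 recruits yield about 38 completers at 20% drop-out, or that 48 covers 16.7%. Use one drop-out rate in the Précis and 9.2. In the Précis and section 3, say consistently whether 40 is the number recruited, randomized or completed.

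The cost is wording in 9.2, the Précis and one sentence of section 3. Conduct and analysis do not change. The stated HRSD and BDI powers fall unless the earlier data support the correlation.
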